4.1 Study Type

Randomized controlled trial with waitlist control design. *Original program was designed for two, 8-week sessions totaling 16 weeks. Unforeseen circumstances (a flood at the facility) shortened the available study period to 14 weeks, so the control condition was shortened and the content condensed and combined to maintain intervention integrity.

4.2 Study Design Overview

- Phase 1: Intervention Group 1 (IG1) receives BRP intervention for 7 weeks while Intervention Group 2 (IG2) receives standard care (waitlist control)
- Phase 2: IG2 receives BRP intervention for 7 weeks while IG1 continues standard care activities
- Total study duration: 14 weeks

4.3 Randomization

Participants will be randomly assigned to IG1 or IG2 within each of the four pre-existing classrooms using a random number generator, with 5-6 students from each classroom assigned to each condition to eliminate potential bias from natural classroom differences.

5. Study Population

5.1 Target Population

Preschool children enrolled at the YWCA Early Learning Center in Cleveland, Ohio, serving under-resourced families with high ACEs exposure

5.2 Sample Size

Target enrollment: n=40 participants (based on total ELC enrollment) Achieved enrollment: n=38 participants Final analytic sample: n=32 participants with complete assessments

5.3 Inclusion Criteria

- Children aged 24-66 months at time of enrollment
- Enrolled at YWCA Early Learning Center during study period
- Parent/caregiver consent for participation
- Ability to participate in group activities

5.4 Exclusion Criteria

- Limited English-speaking fluency requiring translator services
- Parent-reported cognitive delays or medical conditions preventing independent participation in program groups
- Inability to provide informed consent

5.5 Withdrawal Criteria

- Parent/caregiver request for withdrawal
- Child safety concerns identified during intervention
- Consistent non-attendance preventing meaningful intervention participation
- Development of medical condition preventing continued participation

6. Interventions

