6.2 Standard Care Control Condition

Purpose: Control for positive researcher interaction effects while providing beneficial activities

Duration: Concurrent with BRP intervention periods **Content:** School readiness skills supplementing existing curriculum **Weekly Domains:**

- Perceptual motor skills
- Fine motor skills (tool use and coloring)
- Problem solving
- Teamwork and coordination
- Motor planning

Staffing: One licensed occupational therapist

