8.3 Missing Data Handling

Approach: Listwise deletion for each analysis **Rationale:** Participants included only with complete baseline and outcome data for each specific measure **Impact:** Sample sizes range from n=17-19 for primary ANCOVA analyses (8-10 participants per group)

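### Withdrawal for non-attendance after randomisation, with no outcome follow-up planned, lets attendance decide who enters the week-7 ANCOVA and may do so unequally between the arms

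*Combined protocol and SAP*

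**What the plan says.** Children are randomised to IG1 or IG2 within classrooms (4.3). In Phase 1, "Intervention Group 1 (IG1) receives BRP intervention for 7 weeks while Intervention Group 2 (IG2) receives standard care (waitlist control"; in Phase 2, "IG2 receives BRP intervention for 7 weeks while IG1 continues standard care activities" (4.2).

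Section 5.5 lists four grounds for withdrawal. Two are worded around the intervention: "Consistent non-attendance preventing meaningful intervention participation" and "Child safety concerns identified during intervention". The section does not say how much non-attendance counts, in which arm or period, or whether the child leaves the sessions or the study.

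The primary analysis of the standardized measures (8.2.1) is an ANCOVA of week-7 scores, IG1 against the IG2 waitlist, adjusted for baseline. Section 8.3 applies listwise deletion: "Participants included only with complete baseline and outcome data for each specific measure". No as-randomised analysis set is defined, and no section says that withdrawn children are still assessed. Section 9.1 has caregivers complete the standardized forms.

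**The concern.** Attendance is observed after allocation and can be affected by the assigned condition. If poor attenders are withdrawn and their week-7 forms are not sought, the ANCOVA no longer compares the groups as randomised.

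The effect may also differ by arm. Before week 7 only IG1 receives BRP. If intervention participation in 5.5 means BRP, an IG1 child who stops coming in week 3 can be withdrawn before the endpoint, while an equally poor attender in IG2 has no BRP sessions to miss and stays in. The safety ground is worded in the same way. IG1 would then be represented by children who took up and tolerated BRP, and IG2 by all available children. If the missing IG1 children would have done worse, the contrast is shifted towards BRP.

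The loss is avoidable for these measures, because a caregiver can complete the forms whether or not the child attends sessions.

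**Working it through.** **No plan figure to reproduce.** The documents give no count of withdrawals under 5.5, by reason or by arm. What follows is a reading of the text and then an illustration with assumed inputs.

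**1. To which arm does the rule apply before week 7?**

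- Towards BRP only: 7.1.2 sets intervention periods against control periods. 8.2.1 labels IG1 as intervention and IG2 as waitlist control, and separates tests of intervention effects from tests of control-period effects. 6.1 fixes three BRP sessions a week, whereas 6.2 gives no session frequency against which control non-attendance could be judged.
- Towards both arms: the control condition is itself therapist-led activity, described under the chapter on interventions, with the purpose "Control for positive researcher interaction effects while providing beneficial activities". Both arms are named as intervention groups, and the weekly attendance review in 11.3 is not limited to one arm.

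The first reading is the more natural one, but the text does not settle it.

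**2. Removal in IG1 only.** Let p be the fraction of IG1 withdrawn and δ the amount by which their week-7 outcome would be worse than that of the retained children, in SD. If the retained mean is m, the mean of all IG1 children is (1 − p)m + p(m − δ) = m − pδ. The retained mean is therefore too favourable by p × δ.

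Assumptions: 19 children per arm (38 enrolled in 5.2, divided by 2), 2 to 4 withdrawn, δ of 0.5 to 1.0 SD.

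| Withdrawn | p | δ = 0.5 | δ = 1.0 |
|---|---|---|---|
| 2 of 19 | 0.105 | 0.053 | 0.105 |
| 3 of 19 | 0.158 | 0.079 | 0.158 |
| 4 of 19 | 0.211 | 0.105 | 0.211 |

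Against the effects quoted in 8.1, this is 10% to 40% of d = 0.53 (0.053/0.53 and 0.211/0.53) and 8% to 31% of d = 0.68 (0.053/0.68 and 0.211/0.68).

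If low attenders did better, the sign changes: 2/19 × (−0.5) = −0.053 SD.

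These values are before baseline adjustment. The ANCOVA removes whatever part of the deficit the baseline score already predicts; the documents do not allow that part to be estimated.

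**3. Removal in both arms.** If BRP has no effect and the same kind of child is removed from each arm, there is no bias from prognosis. If BRP helps attenders only, the effect in all randomised children is still overstated. With an assumed 16% of low attenders, an effect of 0.53 in attenders and 0 in the rest, the all-randomised effect is 0.84 × 0.53 = 0.445. Attenders alone give 0.53, a difference of 0.085 SD.

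**4. Effect on the test.** Section 8.3 gives 8 to 10 per group; take 9. Then SE = √(2/9) = 0.471 SD. For a bias b, the two-sided type I error is approximately 1 − Φ(1.96 − b/SE) + Φ(−1.96 − b/SE). For b = 0.05, 0.10 and 0.20 SD this is 5.1%, 5.5% and 7.1%, against a nominal 5.0%.

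**5. Context.** Of 38 enrolled, 17 to 19 enter the primary ANCOVA (8.3). So 19 to 21 children, or 50% to 55%, are absent, with no split by arm. The text attributes this to incomplete data; how many, if any, were withdrawn under 5.5 is not stated.

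**The case against.** A reader might infer that the rule removes children only from the BRP arm and so makes the comparison favour BRP. The documents support neither as a certainty. The arm restriction is one reading of ambiguous wording (step 1). The direction depends on how low attenders would have scored, on which the documents are silent.

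It can also be said that 5.5 does not equate withdrawal with exclusion from analysis. Section 8.3 excludes on missing data, not on withdrawal status, so a non-attender whose caregiver returned the week-7 form could be analysed under the plan as written. That is correct. The harm arises only if forms were not sought after withdrawal. But nothing in the plan says that they would be, and withdrawal without provision for follow-up leaves this to chance.

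The asymmetry does not carry over to GAS. The primary GAS comparison in 8.2.2 sets IG1 in weeks 0–7 against IG2 in weeks 7–14, when each group is on BRP and faces the rule on the same terms.

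It is tempting to read the inclusion criterion "Enrolled at YWCA Early Learning Center during study period" (5.3) as a second route of exclusion for children who leave the centre. An inclusion criterion is naturally judged at entry, and 5.5 does not list leaving the centre. No change to 5.3 is needed.

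Lastly, enrolment is complete, so new wording cannot change who was followed. This limits the remedy but does not remove it: the analysis set and the reporting can still be put right.

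**Conclusion.** The concern holds in conditional form. The plan allows withdrawal on a behaviour seen after randomisation, plans no follow-up of those withdrawn, and analyses only children with complete forms. For the week-7 standardized measures the resulting exclusion may differ by arm, plausibly towards BRP. Applied to both arms, it would still select on behaviour that the assigned condition can influence.

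The size is not known. The range of 0.05 to 0.21 SD rests wholly on the assumed 19 per arm, 2 to 4 withdrawals, all in IG1, and a deficit of 0.5 to 1.0 SD, and it ignores baseline adjustment. The effect on type I error would be modest, and the documented loss of half or more of the enrolled children is the larger issue. The point still deserves correction, because the exclusion is avoidable, the remedy is cheap, and groups of 8 to 10 are sensitive to one or two selective losses.

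**What to change.** - **5.5:** State that non-attendance, or any other reason for ending sessions, does not end outcome follow-up. Seek the week-7 and week-14 caregiver forms unless the caregiver withdraws consent. Leave the reasons for ending sessions, including the safety and medical ones, as they are. State to which arm and period the attendance rule applied.
- **8.2.1:** Analyse every randomised child with baseline and week-7 forms in the assigned group, regardless of sessions attended. An analysis restricted by attendance is supportive only.
- **Data already collected:** Include any withdrawn child whose forms exist, and report withdrawals by arm and reason. Enter the change as a dated amendment with its rationale, as 13.1 requires, so that the text does not misdescribe the rule that was in force.

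The cost is a few sentences, a few extra form follow-ups where these are still possible, and possibly a slightly smaller estimated effect because non-attenders are kept.

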6.1 Building Resilience Program (BRP) Intervention

Duration: 7 weeks (modified from original 8-week protocol due to facility closure) **Frequency:** 3 sessions per week **Session Length:** 30-45 minutes **Setting:** Separate room from regular classroom **Group Size:** 5-6 participants per group

6.1.1 BRP Weekly Themes:

- Week 1: Introduction to Resilience
- Week 2: Identifying and Communicating Emotions
- Week 3: Emotional Regulation
- Week 4: Coping Strategies for Self-Regulation: Body and Hands
- Week 5: Coping Strategies for Self-Regulation: Ears, Eyes and Mouth
- Week 6: Coping Strategies for Self-Regulation: Breath Awareness
- Week 7: Applying Positive Coping Strategies

6.1.2 Staffing

Each BRP group will be led by:

- One licensed occupational therapist
- One occupational therapy doctoral capstone student
- 2-3 occupational therapy doctoral research students

6.2 Standard Care Control Condition

Purpose: Control for positive researcher interaction effects while providing beneficial activities

Duration: Concurrent with BRP intervention periods **Content:** School readiness skills supplementing existing curriculum **Weekly Domains:**

- Perceptual motor skills
- Fine motor skills (tool use and coloring)
- Problem solving
- Teamwork and coordination
- Motor planning

Staffing: One licensed occupational therapist

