6.3 Caregiver Intervention Component

Duration: 3 caregiver-only sessions and one joint child-caregiver sessions over 8-week period (reduced from weekly caregiver sessions to accommodate participation challenges) **Format:** In-person group sessions **Staffing:** Occupational therapists and occupational therapy students

6.3.1 Caregiver Session Schedule:

1. **Pre-intervention meeting:** BRP and study description, introduction to resilience, highlights from Inside Out movie, Zones of Regulation overview, Q&A
2. **Week 3 session:** Family resilience, high vs. low resilience, resiliency BINGO activity, Kawa River model, Q&A
3. **Week 6 session:** Adaptive vs. maladaptive behaviors, coping strategies, mindfulness, sensory processing and "sensory solutions," community resources
4. **Post-intervention meeting:** Child and self-advocacy, joint plant activity, program review

6.3.2 Participation Requirements:

- Caregivers attend sessions during their child's intervention period only
- Both post-intervention periods required for complete assessment battery
- Attendance at weeks 3 and 6 sessions only when child participating in BRP intervention

7. Outcome Measures

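### The control condition is said to control for researcher interaction, but adult and caregiver contact is planned to be unequal, so the week-7 contrast measures the whole BRP package

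*Combined protocol and SAP*

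**What the plan says.** Section 6.2 (Standard Care Control Condition) states the aim of the comparator: "Purpose: Control for positive researcher interaction effects while providing beneficial activities". Its staffing line reads "Staffing: One licensed occupational therapist". It says that the control runs alongside the BRP periods, but gives no group size, session length or session frequency.

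Section 6.1.2 says that each BRP group is led by "One licensed occupational therapist", "One occupational therapy doctoral capstone student" and "2-3 occupational therapy doctoral research students". Section 6.1 sets "5-6 participants per group" and "3 sessions per week", with sessions of 30-45 minutes for seven weeks.

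Section 6.3 adds three sessions for caregivers alone and one shared with the child. Section 6.3.2 restricts them: "Caregivers attend sessions during their child's intervention period only". It repeats the restriction for weeks 3 and 6 in particular.

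Section 8.2.1 compares IG1 (on BRP) with IG2 (on waitlist control) at week 7. The covariates are baseline scores and any maturation effect seen in IG2. Section 9.1 says that parents or caregivers complete the standardized forms.

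**The concern.** An activity control that is meant to deal with researcher interaction has to give children in both arms broadly similar contact with the study team. Here the difference in contact runs in the same direction as the treatment. IG1 has more adults in the room and has the caregiver sessions; IG2 has one therapist and no week 3 or week 6 caregiver session.

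This bears on the outcomes as well as on the children. The caregivers who attend the sessions, which cover resilience, coping and adaptive behaviour, also rate the child at week 7. A difference in favour of IG1 could reflect the content, the extra adult attention, the caregivers' changed view of the child, or a mixture. A reader who takes the purpose line in 6.2 at face value would believe that attention had been dealt with.

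**Working it through.** The documents give no figure for contact to reproduce, so the check counts planned contact from each section.

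**1. Adults per session.** BRP (6.1.2): 1 therapist + 1 capstone student + 2 to 3 research students = 4 to 5. Control (6.2): 1. Ratio: 4/1 = 4 to 5/1 = 5.

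**2. Children per adult.** BRP, with 5-6 children (6.1): 5/5 = 1.0 to 6/4 = 1.5. Control: not computable, because 6.2 gives no group size. If control groups also had 5-6 children (assumption), the figure would be 5/1 = 5 to 6/1 = 6.

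**3. Contact time.** BRP: 7 weeks × 3 sessions = 21 sessions. Session time is 21 × 30/60 = 10.5 hours to 21 × 45/60 = 15.75 hours. Adult-hours per group are 4 × 10.5 = 42 to 5 × 15.75 = 78.75. Control: not computable from 6.2. On BRP's schedule (assumption), one therapist would supply 10.5 to 15.75 adult-hours per group.

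For one therapist to equal BRP's adult-hours with groups of BRP's size, control sessions would have to total 42 to 78.75 hours, which is 42/7 = 6 to 78.75/7 = 11.25 hours a week. On BRP's schedule, control groups would instead have to be 1.0 to 1.5 children. Section 6.2 states nothing of either kind.

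**4. Caregiver contacts up to week 7.** IG1: up to 3 + 1 = 4. IG2: 0 on the plain reading of 6.3.2. If IG2 caregivers also came to the opening and closing meetings of phase 1, the figure would be 2, because only weeks 3 and 6 are excluded beyond doubt. The gap is 4 − 2 = 2 to 4 − 0 = 4.

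**5. What the week-7 model can estimate.** Write the expected IG1 − IG2 difference as content + adult contact + caregiver sessions. All three are fixed by arm, so the group coefficient estimates only their sum. Randomization within classrooms balances the children, not the conditions assigned to them. Baseline and maturation covariates leave the sum unchanged. A covariate for planned contact would not help, since it would be identical to the group indicator.

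**6. The other primary analysis.** The GAS ANCOVA in 8.2.2 sets IG1 in weeks 0-7 against IG2 in weeks 7-14. Both groups are then on BRP, with the same planned staffing and caregiver sessions. The imbalance does not enter that contrast.

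**The case against.** The strongest reply is that a package comparison is legitimate, particularly in a pilot. Section 2.1 asks about the effects of the program, and staffing and caregiver sessions are parts of it. No section claims that the trial isolates BRP content. This stands: the contrast is valid for the package. It does not rescue the purpose line in 6.2, which gives the control a role that its staffing cannot fill.

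A second reply is that the control does provide interaction. A therapist leads it, and under 7.1.2 and 9.1 research team members make weekly GAS observations in both periods. This also stands, and it is why the finding is partial control and not absence of control. The documents do not say how far observers interact with children, and observation is planned for both arms, so it is not shown to close the gap.

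A third reply is that IG2 caregivers may attend at week 7, because 6.3.2 says that both post-intervention periods are needed for the full assessment battery. That is possible. It does not touch the week 3 and week 6 sessions.

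Several stronger readings are tempting but not supported:
- A reader might infer a bias of a given size, or an inflated false-positive rate. The documents give neither the control's dose nor any effect of attention from which to calculate one.
- A reader might take the shorter list of control domains, set against the BRP weekly themes, as evidence of less contact. A domain can span more than one week, so the lists say nothing about contact.
- A reader might extend the point to the paired tests in 8.2.1. Those are within-group changes; no paired contrast of control period against BRP period is planned.

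**Conclusion.** The point holds for the week-7 ANCOVA on the standardized measures. Section 6.2 states a property that the design has at most in part. The analysis supports a statement about the BRP package against a lower-contact activity. It does not support a statement that attention effects have been ruled out, or that the content is responsible.

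What can be sized from the documents is the planned imbalance: 1 adult against 4-5 in the staffing lines, and 2 to 4 fewer caregiver contacts in IG2 by week 7. Describing the control as lower-contact assumes that it did not offset its staffing with much smaller groups or much longer sessions, and 6.2 mentions neither. The caregiver imbalance does not depend on that assumption. The bias in the outcome scale cannot be sized.

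A reader might infer that the trial is uninterpretable. It is not: children are randomized, the package comparison remains, and the GAS contrast is free of this particular problem.

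**What to change.** - **Section 6.2.** Replace the purpose line with wording such as: *the control provides a structured therapist-led activity and does not equalise adult or caregiver contact with BRP*.
- **Section 8.2.1 and the report.** State the week-7 conclusion as the effect of the BRP package (content, staffing and caregiver sessions) over a lower-contact activity. Do not claim that attention effects are ruled out.
- **Report.** Tabulate delivered contact by arm: sessions attended, plus adults present and minutes where they were recorded. The attendance review in 11.3 should supply the session counts. The plan does not promise records of adults present or minutes, so any gap should be stated.

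Sections 5.2 and 8.1 already report the achieved sample and post-hoc power, so the remedy lies in wording and reporting. The cost is a few lines of text, one descriptive table and a less favourable conclusion.

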6.3 Caregiver Intervention Component

Duration: 3 caregiver-only sessions and one joint child-caregiver sessions over 8-week period (reduced from weekly caregiver sessions to accommodate participation challenges) **Format:** In-person group sessions **Staffing:** Occupational therapists and occupational therapy students

6.3.1 Caregiver Session Schedule:

1. **Pre-intervention meeting:** BRP and study description, introduction to resilience, highlights from Inside Out movie, Zones of Regulation overview, Q&A
2. **Week 3 session:** Family resilience, high vs. low resilience, resiliency BINGO activity, Kawa River model, Q&A
3. **Week 6 session:** Adaptive vs. maladaptive behaviors, coping strategies, mindfulness, sensory processing and "sensory solutions," community resources
4. **Post-intervention meeting:** Child and self-advocacy, joint plant activity, program review

6.3.2 Participation Requirements:

- Caregivers attend sessions during their child's intervention period only
- Both post-intervention periods required for complete assessment battery
- Attendance at weeks 3 and 6 sessions only when child participating in BRP intervention

7. Outcome Measures

7.1 Primary Outcome Measures

7.1.1 Standardized Assessment Battery

NIH Toolbox Parent Report Emotion Measures:

- Negative Affect subdomain (anger, fear, sadness/depression)
- Psychological Well-being subdomain (positive affect, life satisfaction)

PROMIS Early Childhood Measures:

- Flexibility
- Persistence (Note: Curiosity and Frustration Tolerance removed due to ceiling effects)

Pediatric Quality of Life Inventory (PedsQL):

- Physical Functioning
- Emotional Functioning
- Social Functioning
- School Functioning

- Composite Score

Canadian Occupational Performance Measure (COPM):

- Parent proxy report of child's occupational performance
- Used primarily for Goal Attainment Scaling development

